6.1.4 Adjustments for Covariates

Not applicable to this study.

6.1.5 Handling of Dropouts or Missing Data

If a partial date is reported where the day is missing, then the day will be imputed as the first day of the month unless the month is the same month as the first injection then the day will be that of first injection with the month and year remaining the same. If a partial date is reported where the month is missing, then the month will be imputed to January unless the year is the same year as the first injection then the month will be that of first injection with the year remaining the same. If a partial date where both the day and month is missing, follow details as stated previously.

Missing adverse event dates will be imputed using partial date imputation rules as previously described in this Section. Missing data for other parameters will not be imputed for analysis unless otherwise defined.

The primary method for handling missing data for the analysis of the primary and secondary endpoints will be LOCF.

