8.4.5. Adverse Events

Adverse events will be collected from the time the subject signs the informed consent form (ICF) until the final visit/contact with the subject. At each visit/contact, the Investigator or designee is responsible for reviewing, documenting, and reporting events that meet the definition of an AE.

Subjects should be asked a non-leading question in order to avoid bias in eliciting AEs; such as “Have you had any changes in your health since your last visit?” at each visit/contact. It is important to question the subject in a non-leading way about changes in their health or concomitant medication usage since their last visit.

- * For any subject who develops an AE suggestive of a retrovirus-associated disease after FCX-007 treatment, attempts will be made to collect any relevant clinical samples for available RCL testing.
- * For any subject who dies or is diagnosed with a neoplasm after FCX-007 treatment, attempts will be made to collect a biopsy of the neoplastic tissue or pertinent autopsy tissue to assay for available RCL testing by qPCR.

Following the subject’s initial report of an AE, the Investigator or designee is required to proactively follow-up with the subject regarding any previous AE that hasn’t resolved at subsequent visits/contacts.

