8.4.5.2. Reporting Procedure

All AEs observed by the Investigator or site staff or reported by the subject or their caregiver (whether or not attributed to IP), must be fully and completely documented in the subject's source documents and CRF. In the event a subject is withdrawn from the study because of an AE, the primary reason for withdrawal (i.e., due to an AE) must be recorded on the CRF as such.

Each AE requires a complete description including event description (where possible, a diagnosis or if a diagnosis has not been made, individually listed sign(s)/symptom(s)), date of onset and resolution, if applicable, outcome (refer to Section 8.4.5.3), and actions taken to be recorded in the source documents. The Investigator must also assign the following attributes for each AE: its relationship to the IP (refer to Section 8.4.5.4) and severity of the AE (refer to Section 8.4.5.5). The Investigator may be asked to provide follow-up information.

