6.8.2 Adverse Events

All AEs that occur during the study will be recorded and classified on the basis of Medical Dictionary for Regulatory Activities (MedDRA) terminology. Treatment-emergent AEs (TEAEs) are defined as AEs with an onset on or after the date of the first injection. Adverse events noted prior to the first injection that worsen after baseline will also be reported as AEs and included in the summaries.

Treatment-emergent AEs will be summarized by the number of subjects reporting a TEAE, system organ class, preferred name, severity, relationship to FCX-007 (causality), whether within treatment area, and seriousness. When summarizing AEs by severity and relationship, each subject will be counted once within a system organ class or a preferred term by using the event with the highest severity and greatest relationship within each classification.

Serious AEs (SAEs) will be summarized by severity and relationship to investigational product, and individual SAEs will be listed by subject. In addition, a list of subjects who prematurely discontinued from the study due to an AE will be provided.

Listings will be presented for all adverse events as well as for serious adverse events, and adverse events leading to discontinuation from the study.

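### A partial AE onset in the month or year of first injection is moved to the injection date with no check of the recorded end date, so an event known to be pre-treatment can be counted as a TEAE

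*SAP*

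**What the plan says.** SAP 6.1.5 sets out one partial-date rule.

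- Day missing: "the day will be imputed as the first day of the month unless the month is the same month as the first injection", in which case the injection day is used.
- Month missing: January, "unless the year is the same year as the first injection then the month will be that of first injection".
- Both missing: "If a partial date where both the day and month is missing, follow details as stated previously".

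The section then extends the rule to AEs: "Missing adverse event dates will be imputed using partial date imputation rules as previously described in this Section". It does not separate onset from resolution, although Protocol 8.4.5.2 has the site record "date of onset and resolution, if applicable, outcome" for each AE.

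SAP 6.8.2 supplies the classification: "Treatment-emergent AEs (TEAEs) are defined as AEs with an onset on or after the date of the first injection". The end date plays no part in it. Protocol 8.4.5 collects AEs from the signing of consent, and SAP 4.1 expects a Screening Period of about 4-6 months, so pre-injection AEs will be in the database. Protocol 10.4.3 plans to group AEs into pre-treatment events and TEAEs. Neither document gives a separate rule for AE end dates or a check of one AE date against the other.

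**The concern.** Moving a partial onset to the injection date is a cautious way to settle a date that could fall on either side of dosing. It stops being caution when the recorded end date shows that the event finished before dosing, because the imputation then overrides a known fact. It also departs from Protocol 8.4.5.1, under which a TEAE is an AE occurring after administration of the product. Protocol 10.4 makes the SAP operative where the two differ, so the SAP rule would govern.

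The stake is the TEAE tables. SAP 7 limits enrolment to 6 subjects and SAP 8 makes the efficacy analyses descriptive. Safety is then read from raw counts, where one misclassified subject is visible in a row.

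**Working it through.** The documents state no figure on this point, so there is none to reproduce. The check applies the rule as written.

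**Inputs.** The imputation rule (SAP 6.1.5), the TEAE definition (SAP 6.8.2), 6 subjects (SAP 7), and an assumed first injection on 20 Nov 2021. I read a matching month as the same month of the same year.

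**Rule.** Month = recorded month; if missing, the injection month when the year matches, otherwise January. Day = recorded day; if missing, the injection day when month and year match, otherwise 1. TEAE if the imputed onset is on or after the injection date.

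**Onset dates.**

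| Recorded onset | Recorded end | Imputed onset | Class | Comment |
|---|---|---|---|---|
| Nov 2021 | 8 Nov 2021 | 20 Nov 2021 | TEAE | Ended 12 days before injection (20 − 8) |
| 2021 | 5 Aug 2021 | 20 Nov 2021 | TEAE | Ended 107 days before injection (26 + 30 + 31 + 20) |
| Aug 2021 | 10 Aug 2021 | 1 Aug 2021 | Pre-treatment | Correct: month does not match |
| Nov 2021 | Nov 2021 | 20 Nov 2021 | TEAE | Truly ambiguous; cautious result |

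The first two rows are wrong and the last two are acceptable. A Screening Period of 4-6 months before 20 Nov 2021 would begin between 20 May and 20 Jul 2021, so the 5 Aug end date falls inside it.

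**How general this is.** Take an injection on day D, an onset day missing in the injection month, and an end before injection. There are D(D − 1)/2 possible pairs of true start and end day within that month: 28 for D = 8, 105 for D = 15, 435 for D = 30, and none for D = 1. Every pair is classed as a TEAE, because the rule never reads the end date. The same holds for every year-only onset in the injection year with an end before injection. These are counts of possible date pairs, not expected frequencies in the trial.

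**Size.** One misclassified subject out of 6 is 1/6 = 16.7 percentage points in a row where that subject has no other event.

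**End dates (secondary).** Onset 25 Jan 2022 with end Jan 2022 gives an imputed end of 1 Jan 2022, 25 − 1 = 24 days before onset. Onset 10 Sep 2022 (day 253 of the year) with end 2022 gives 1 Jan 2022, 253 − 1 = 252 days before onset. In a 30-day month other than the injection month there are 30 × 31/2 = 465 pairs of start and end day. The imputed end is the 1st, so it precedes every start except the 30 pairs that begin on the 1st: 435/465 = 93.5%.

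**The case against.** The strongest reply has four parts.

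First, the error needs several things together: a Screening Period AE, a partial onset, a match with the injection month (or with the year, if only the year is known), and a known end before injection. Complete onsets and partial onsets elsewhere are unaffected. This stands, and it bounds the point.

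Second, substituting the injection date is deliberately cautious. This stands for ambiguous onsets, but an event recorded as finished before dosing is not ambiguous.

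Third, Protocol 8.4.5.2 requires AE dates, Protocol 11.8.1 provides for queries and for CRFs ready for review within one week of a visit, and Protocol 11.8.1.2 adds validation checks. These make year-only onsets less likely. They do not catch the error: an onset of Nov 2021 with an end of 8 Nov 2021 is consistent as recorded, and the contradiction appears only after imputation.

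Fourth, SAP 6.8.2 lists all AEs and tabulates relationship to FCX-007, so a careful reader may spot the case. The overall TEAE row would still include it.

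Three stronger readings are tempting, and the documents do not support them. A reader might infer that AEs which ended before injection are generally counted as TEAEs; they are only under the conditions above. A reader might call this an earliest-date rule; in the injection month or year it gives the injection date instead, and that substitution causes the TEAE error. A reader might also infer that AE listings will show impossible dates or that end dates distort the tables. SAP 6.8.2 plans no AE duration analysis, TEAE status uses onset only, and neither document says that listings print imputed dates.

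**Conclusion.** SAP 6.1.5, read with 6.8.2, gives a wrong result in one defined case: a partial AE onset in the month (or, if year-only, the year) of first injection, with a recorded end before that injection. Such an AE is known to be pre-treatment but is classed as a TEAE. One event could move a TEAE row by up to about 17 percentage points. That assumes all 6 enrolled subjects are in the safety population and that the subject has no other event in the row. How many partial AE dates exist is not stated, so the actual effect may be nil.

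The end-date part rests on the plain reading that AE dates include end dates. It can produce an end before its start in derived data, but it changes no TEAE count and no planned summary.

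**What to change.** In SAP 6.1.5:

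1. Do not substitute the injection day or month for a partial AE start when the recorded end date, or its latest possible value if partial, is before the first injection. Impute the earliest date compatible with the recorded parts, not before consent if the AE began on study and never after the end date. Class the AE as pre-treatment.
2. Keep the present rule for all other partial onsets, so that ambiguous events remain TEAEs.
3. Limit the rule to AE start dates. Either leave partial end dates unimputed, or impute them to the last possible day and never before the start.

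In the worked examples, onset Nov 2021 with end 8 Nov 2021 becomes 1 Nov 2021. Onset 2021 with end 5 Aug 2021 becomes 1 Jan 2021, or the consent date if the AE began on study. Both are then pre-treatment. The Nov 2021 to Nov 2021 case stays a TEAE, because its latest possible end is 30 Nov.

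The cost is a few sentences in the SAP and a small programming change, with no new data.

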7.1. INCLUSION CRITERIA

Each subject must meet all of the following criteria to be eligible for treatment in this study:

1. Subjects and/or their legal guardian must provide written informed consent, in accordance with federal and/or local laws, before any study procedures occur. In addition, if applicable, a minor child must provide written informed assent in accordance with federal and/or local laws as well as in compliance with the recommendations of the approving Institutional Review Board (IRB), before any study procedures occur.
2. Male or female ≥ 2 years of age at the Screening visit (when consent/assent for study participation is given).
3. Clinical diagnosis of RDEB with confirmation of COL7A1 genetic mutation.
4. At least two eligible persistent non-healing or recurrent wounds identified at Day 1 (Visit 2):
 - Each wound must have an approximate minimum area of 5 cm² (subjects 2 to 6 years of age at time of consent) or 10 cm² (subjects 7 years of age or older at time of consent) and a maximum of 50 cm²
 - Wound site was monitored for at least 12 weeks prior to Day 1 (Visit 2) and wound is open (unhealed)
 - The following wounds are excluded:
 - Wounds on a mucous membrane, the face, hands, feet, or fully across joints;
 - Wounds with active infection or evidence of active infection;
 - Wounds that have been previously treated with a gene therapy intervention.
5. Female subjects of childbearing potential and post-pubertal male subjects engaging in sexual activity that could lead to pregnancy who agree to using at least one of the following adequate birth control regimens while in the study and for 6 months after last dose of FCX-007 is administered:
 - Male partner with vasectomy, OR
 - Male condom AND partner use of one of the contraceptive options below:

- Spermicide
- Intrauterine device or intrauterine system
- Oral contraceptive, either combined or progestogen alone
- Contraceptive subdermal implant (e.g., Norplant[®])
- Injectable progestogen (e.g., Depo-Provera[®])
- Contraceptive vaginal ring (e.g., NuvaRing[®])
- Transdermal contraceptive patches (e.g., Ortho Evra[®])
- Subjects of childbearing potential who are abstinent are eligible, but they must agree to use one of the birth control regimens listed above if they begin engaging in sexual activity that could lead to pregnancy during the study.

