The main principle of care in RDEB is to manage blisters and wounds, control infection and prevent complications. Lack of COL7 causes a delay in cutaneous wound healing, increased risk

of infection, inflammation, and development of a continuum of chronic wounds with similar biology and physical characteristics, that can be classified as either chronic open wounds that stay open for ≥ 12 weeks (persistent non-healing wounds) or recurrent open wounds defined as areas that heal but then easily re-blister due to repetitive trauma ([4]; [5]; [6]); personal communication [name], MD, PhD). Studies have documented the extensive distribution of wounds and show that patients with RDEB generalized severe subtype may have skin wounds on any surface, especially sites exposed to mechanical stress [5]. The natural history of wounds in EB study by Solis, et al. demonstrated that persistent non-healing wounds have a duration of ≥ 7 years and as suggestive of their description, these wounds never heal. In contrast, the majority of recurrent wounds heal within 3 weeks but re-blister/open within 3 weeks [6].

The negative psychosocial impact of chronic wounds in patients with RDEB, and the medical and financial burden of wound care due to chronic wound infections, pain, and pruritus is well documented ([7]; [8]; [9]; [10]). Optimal treatment of RDEB will likely involve a combination of therapies. Given that the essential skin pathology in RDEB is a lack of COL7 in the basement membrane, Fibrocell has developed FCX-007, an autologous gene and cell therapy product that is intradermally administered and may be used for all RDEB patients, regardless of mutation type, for chronic non-healing and recurrent wounds. The safety and efficacy of FCX-007 is being studied for the treatment of wounds in patients with RDEB.

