6. STATISTICAL AND ANALYTICAL PLANS

6.1 General Methodology

All statistical processing will be performed using SAS® unless otherwise stated. No interim analyses are planned. The primary analysis will occur once all subjects have completed Week 24. No statistical testing will be performed.

Descriptive statistics will be used to provide an overview of the efficacy and safety results. For categorical parameters, the number and percentage of subjects in each category will be presented. For continuous parameters, descriptive statistics will include n (number of subjects), mean, standard deviation (SD), median, minimum and maximum.

The primary method of handling missing efficacy data will last observation carried forward (LOCF).

Efficacy analysis will be performed on the Full Analysis Set (FAS) population.

The number of subjects in each analysis set will be summarized. Reasons for study withdrawal during the treatment period will be summarized using frequencies and percentages.

Reported AEs, medical history terms and prior and concomitant procedures and therapies will be classified on the basis of Medical Dictionary for Regulatory Activities (MedDRA) terminology. Prior and concomitant medications will be classified on the basis of World Health Organization Drug Dictionary (WHO-DDE) terminology.

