6.1.3 Visit Windowing

Data will be summarized based on nominal visit indications with the exception of data captured at early termination and unscheduled visits; data from early termination and unscheduled visits will be summarized based on mapped visit values. The analysis windows for early termination and unscheduled visits are presented in the following table.

Analysis Windows for Early Termination and Unscheduled Visit Mapping

Scheduled Visit	Protocol Specified Window	Analysis Window
Week 12	Week 11 to 16 (Day 78 to 113)	Week 6 to 18 (Day 43 to 126)
Week 24	Week 23 to 28 (Day 162 to 197)	Week 18 to 30 (Day 127 to 210)
Week 36	Week 35 to 40 (Day 246 to 281)	Week 30 to 42 (Day 211 to 294)
Week 48	Week 47 to 52 (Day 330 to 365)	Week 42 to 54 (Day 295 to 379)

Early termination and unscheduled visits will not be mapped to the Week 22 visit.

Data collected at early termination and unscheduled visits prior to study day 78 will not be analyzed, with the exception of those identified as baseline values. Data from assessments performed after study day 379 will not be included in analyses.

The definition for the study day included in each study window is defined as below:

Study Day prior to Day 1 = Visit Date – Day 1 Date

Study Day on or after Day 1 = Visit Date – Day 1 Date + 1

If an assessment's mapped visit is a visit at which the subject has data from a scheduled visit present, or if no analyses are planned for the assessment at the mapped visit, the data collected at the early termination or unscheduled visit will be presented in listings only.

In the event of multiple values from unscheduled or early termination assessments within an analysis window, the value closest to the scheduled visit target study day will be used for analyses. If two values tie as closest to the time point (for example, one value is before and the other value is after the time point), then the later value will be selected.

Data collected at all visits will be included in the data listings with visit presented as reported by the site.

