6.7 Analysis of Efficacy

6.7.1 Primary Efficacy Analysis

The primary efficacy endpoint is complete wound closure of the First Wound Pair at Week 24, with confirmed complete wound closure at serial assessments at Weeks 22 and 24. The number and percentage of complete closures will be reported by treatment group.

The primary efficacy analysis will be presented for the FAS population.

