6.7.5 Sensitivity Analyses

Sensitivity analyses will be included in order to assess the impact of missing data.

In the event of missing Week 24 WAs (with confirmatory closure at Week 22) for either wound, sensitivity analyses will consider these wounds as failures.

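### The primary endpoint needs closure confirmed at Weeks 22 and 24, but LOCF is the primary missing-data rule with its unit undefined; applied visit by visit, one reading can stand for both

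*SAP*

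**What the plan says.** **Endpoint.** SAP 6.7.1 and Protocol 10.4.2.1 define the primary endpoint as First Wound Pair closure at Week 24, "with confirmed complete wound closure at serial assessments at Weeks 22 and 24". Two readings are required.

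**Primary missing-data rule.** Protocol 10.7 names LOCF and leaves the detail to the SAP, which Protocol 10.4 makes the governing text. SAP 6.1 repeats LOCF, and SAP 6.1.5 says: "The primary method for handling missing data for the analysis of the primary and secondary endpoints will be LOCF". Neither document says whether the carried unit is a visit's reading or the two-visit outcome, or whether one reading may fill both visits.

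**Failure rule.** SAP 6.7.5 treats missing wounds as failures, but only in sensitivity analyses. Its trigger is worded "In the event of missing Week 24 WAs (with confirmatory closure at Week 22) for either wound".

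**Windowing.** Under SAP 6.1.3, an early-termination or unscheduled reading from Day 127 to 210 maps to Week 24. It goes to listings only if, among other conditions, its "mapped visit is a visit at which the subject has data from a scheduled visit present". For the confirming visit: "Early termination and unscheduled visits will not be mapped to the Week 22 visit".

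**Assessments.** SAP 4.1.3 requires blinded closure assessment at Weeks 12, 22 and 24, before any injection at that visit. At Weeks 36 and 48 blinding is only preferred.

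**Size and inference.** SAP 6.1, 7 and 8 give 6 enrolled subjects, no testing, and descriptive primary and secondary summaries.

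**The concern.** The confirmation requirement is there so that a single closed reading does not count as a success. An undefined LOCF rule can undo that. In the Schedule of Events (Protocol Table 3), Week 12 is the only scheduled closure assessment before Week 22. A wound closed at Week 12 and not seen again would therefore be closed at both later visits under visit-by-visit LOCF, and would be reported as confirmed with neither reading observed. That Week 12 reading also precedes the second injection session.

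With no test and no interval planned, the counts of confirmed closures by arm are the primary result. At stake is whether the headline count matches the endpoint it is labelled with.

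**Working it through.** **1. The plan's own figure.** SAP 7 gives 85% power for 24 pairs at 60% v 10% closure with 70% discordance. Summing over m ~ Bin(24, 0.70) discordant pairs, with an exact two-sided binomial test at 0.05 and success probability 0.60/0.70, gives 0.851. The figure reproduces. The point does not depend on it; only its cell probabilities are used below.

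**2. What each rule does with a missing reading.**

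| Pattern | Visit-by-visit LOCF | Required readings observed | SAP 6.7.5 |
|---|---|---|---|
| Week 12 closed; Weeks 22 and 24 missing | Confirmed closed | 0 of 2 | Failure |
| Week 22 closed; Week 24 missing | Confirmed closed | 1 of 2 | Failure |
| Week 12 closed; Week 22 missing; Week 24 closed | Confirmed closed | 1 of 2 | Unclear |
| Week 12 closed; Week 22 missing; closed reading mapped to Week 24 | Confirmed closed | At most 1 of 2 | Unclear: Week 24 may not count as missing |

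If LOCF instead applies to the two-visit outcome, that outcome first exists at Week 24. Nothing earlier can be carried, and the rule gives no result.

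In the last row the mapped reading can be as early as Day 127, which is 169 − 127 = 42 days before target Week 24. It need not be blinded: Protocol 7.6.2 asks for the Visit 6 assessments in early leavers.

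**3. Age of a carried Week 12 reading.** Target days are 12 × 7 + 1 = 85 and 24 × 7 + 1 = 169. The age at Week 24 is 169 − 85 = 84 days. Across the Week 12 window (Day 78 to 113) it runs from 169 − 113 = 56 to 169 − 78 = 91 days.

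**4. Size per wound.** With 6 subjects in the full analysis set (FAS), one wound is 100/6 = 16.7 points of its arm. With 5 it would be 100/5 = 20.0.

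**5. Gap between the two rules (LOCF minus missing-as-failure in the arm difference), for subjects last seen at Week 12.** The documents give no dropout rate, so one or two such subjects is an assumption, as are the Week 12 rates.

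*Planning rates.* Treated-only closure is (0.70 + 0.50)/2 = 0.60, control-only 0.70 − 0.60 = 0.10, both 0.60 − 0.60 = 0, neither 0.30.
- One subject: +16.7 points (probability 0.60), 0 (0.30), −16.7 (0.10). Mean (0.60 − 0.10) × 16.7 = 8.3.
- Two subjects: +33.3 (0.60² = 0.36), +16.7 (2 × 0.60 × 0.30 = 0.36), 0 (0.30² + 2 × 0.60 × 0.10 = 0.21), −16.7 (2 × 0.30 × 0.10 = 0.06), −33.3 (0.10² = 0.01). Mean 16.7.

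*Phase 1/2 Week 12 result* (Protocol 4.2.1.1: 8/10 treated, no control wound; this counts closure of 90% or more, so it is looser than this endpoint).
- One subject: +16.7 (0.80) or 0 (0.20). Mean 13.3.
- Two subjects: +33.3 (0.64), +16.7 (0.32), 0 (0.04). Mean 26.7.

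**6. Which rule is nearer the truth.** Expected arm difference in points, with missingness unrelated to outcome:

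| Scenario | Missing of 6 | Truth | Failure rule | LOCF |
|---|---|---|---|---|
| 60% v 10% at Week 12 and Week 24 | 1 | 50 | 5/6 × 50 = 41.7 | 50 |
| Same | 2 | 50 | 4/6 × 50 = 33.3 | 50 |
| 60% v 10% at Week 12, no difference at Week 24 | 1 | 0 | 0 | 1/6 × 50 = 8.3 |
| Same | 2 | 0 | 0 | 2/6 × 50 = 16.7 |

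Neither rule is less biased in every case.

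**The case against.** The strongest reply is that this is only a request for clarification. The endpoint wording can be read as demanding observed readings. The failure analysis is already planned, and all visits are listed, so with 6 subjects both counts can be read side by side. Losing both readings is made less likely by a Week 22 assessment that can be done remotely or from same-day images (Protocol 8.5.2.3), weekly home imaging through Week 24 (Protocol 8.3.2), and continued assessments after FCX-007 is stopped (Protocol 7.6.2). The replacement rule has its own cost: it scores an observed blinded Week 24 closure as not confirmed when only Week 22 was missed.

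Most of this stands, and it limits the size of the point. It does not settle which count is the headline, or what happens when Week 22 alone is missing.

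Three stronger readings are tempting but unsupported:
- *A carried value could be of any age.* SAP 6.1.3 drops early-termination and unscheduled data before Day 78 (baseline aside), no closure assessment is scheduled before Week 12, and target wounds must be open at Day 1. A carried closure cannot be much older than Day 78, unless a nominal Week 12 visit was held early.
- *Most analysed wounds would have reopened.* SAP 2 says "the majority of recurrent wounds heal within 3 weeks but re-blister/open within 3 weeks", but that is the natural history of recurrent wounds. They are eligible (Protocol 7.1), yet the First Pair rule (Protocol 8.3.1.2, SAP 4.1) favours the wounds open longest with the least change in area.
- *LOCF inflates the effect.* It does if a treated wound closed at Week 12 later reopens. It understates the effect if a treated wound closes after the second session, or if a control wound's temporary closure is carried.

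**Conclusion.** The point holds as a mismatch between the endpoint and its primary missing-data rule, and should be fixed before the analysis. Applied to each visit, LOCF can report a confirmed closure with one or neither required reading observed. Applied to the two-visit outcome, it gives no result. The failure rule covers a missing Week 24 only as a sensitivity analysis, and does not clearly cover a missing Week 22 with Week 24 observed.

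The size is 16.7 points of an arm per affected wound, if all 6 enrolled subjects are in the FAS. The distributions in the working measure the gap between two rules under assumed missingness; they are not estimates of bias in this trial. No missing visit is documented, so the effect may be nil. No p-value or error rate is affected, because none is planned. The case for change is fidelity to the endpoint definition, not lower bias in every scenario.

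**What to change.** Amend SAP 6.1.5, 6.7.1 and 6.7.5:

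- In the primary summary, count a First Pair wound as confirmed closed only if a Blinded Investigator observed closure at both Week 22 and Week 24. Count every other wound, including one missing Week 22 alone, as not confirmed closed.
- Let a reading mapped to Week 24 under SAP 6.1.3 count only if it was blinded and fell within the protocol Week 24 window (Day 162 to 197). Otherwise show it in listings.
- Make LOCF the sensitivity analysis and state its unit: visit reading or two-visit outcome.
- Report per arm how many wounds lack either reading.

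The cost is SAP wording. Both rules are already planned, so mainly their roles change, and no new data are needed. The downside is a conservative primary count. If closure is stable after Week 12, it understates treated closure, and at planning rates the expected difference falls from 50 to 41.7 or 33.3 points with one or two of 6 subjects missing. LOCF as the sensitivity analysis shows the range.
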